1. PROTOCOL SYNOPSIS

Study Title	A Phase 2 Randomized, Single-Blind Study of a Single Dose of Peginterferon Lambda-1a (Lambda) Compared with Placebo in Outpatients with Mild COVID-19
Sponsor	Stanford University
Description	Single-blind randomized controlled trial
Study Objectives	
 1. To evaluate the efficacy of subcutaneous (SC) injections of a single dose of 180 mcg of Peginterferon Lambda-1a compared with placebo in reducing the duration of viral shedding of SARS-CoV-2 virus in patients with uncomplicated COVID-19 disease. 2. To evaluate the efficacy of subcutaneous injections of a single dose of 180 mcg of Peginterferon Lambda-1a compared with placebo, in reducing SARS-CoV-2 viral loads and the duration of symptoms, hospitalizations, or ED visits in patients with uncomplicated COVID-19 disease. 3. To evaluate the safety and tolerability of subcutaneous injections of a single dose of 180 mcg of Peginterferon Lambda-1a compared with placebo.
Scientific rationale	
Recently, a novel corona virus has been identified as the causative pathogen of a rapidly spreading infection associated with pneumonia and severe acute respiratory syndrome. COVID-19, originally identified in Wuhan in the Hubei province of China, has now spread across the globe and has been declared by the WHO as a global pandemic. While the majority of infected patients display mild symptoms if any, death rates of up to 4% due to development of severe acute respiratory syndrome (COVID-19 SARS), have been reported in patients with co-morbid conditions and in the elderly population. With the unprecedented global health and economic threats imposed by COVID-19, development of therapies capable of suppressing or eradicating this emerging pathogen has become an urgent unmet medical need.
 
The interferon (IFN) system represents a major element of the innate immune response against viral infections. Virus-induced IFN is a complex mixture of biologically active molecules, which includes type I and type III IFNs. Binding of type I IFN and type III IFN to their cognate receptor complexes triggers signaling cascades that result in the activation of a large number of genes, many of which encode antiviral proteins. Type III IFN (i.e. IFN-λ) uses a distinct receptor complex (IL28R) for signaling which appears to be expressed on only a few cell types, including epithelial cells in the respiratory and gastrointestinal tract, resulting in demonstrated improved tolerability profile. Based on IFN-λ's more limited receptor distribution and therefore expected improved tolerability profile, a pegylated form of recombinant Peginterferon Lambda-1a (Lambda) has been developed for the treatment of chronic viral hepatitides such as hepatitis C, hepatitis B and recently also hepatitis D. Lambda has so far been administered in over 3000 patients in multiple clinical trials, showing a good safety and tolerability profile with varying degrees of antiviral efficacy. The presence of IL28R in the epithelial cells of the lungs and respiratory tract has also evoked research on the potential role of IFN-λ in

	possible mitigation of viral induced respiratory infections. Indeed, studies in animal models have shown that IFN-λ inhibits replication of respiratory viruses such as influenza as well as the SARS-coronavirus. The use of Lambda for treatment of COVID-19 infection has not yet been explored.
Participants and Sample Size	We will enroll 120 patients ages 18-64 with confirmed COVID-19 infection diagnosed by molecular diagnostic assay.
Clinical Site	The study will be conducted at the Stanford University School of Medicine
Study duration	The total anticipated duration of the study for each patient is up to 28 days, with optional long-term follow-up to 10 months following recruitment. The planned duration of the entire study is 12 months.
Selection Criteria	
Inclusion Criteria
 
 1. Age \geq 18 years and \leq 75 years at the time of the assessment 2. Able and willing to understand the study, adhere to all study procedures, and provide written informed consent 3. Diagnosis of COVID-19 disease: 
 a. If symptomatic, presence of mild to moderate symptoms without signs of respiratory distress, with FDA-cleared molecular diagnostic assay positive for SARS-CoV-2 within 72 hours from swab to the time of commencing informed consent: b. If asymptomatic, initial diagnosis of SARS-CoV-2 infection with positive FDA-cleared molecular diagnostic assay obtained no more than 72 hours from initial swab to the time of commencing informed consent 
Exclusion Criteria:
 
 1. Patients who are hospitalized for inpatient treatment or currently be evaluated for potential hospitalization at the time of initiation of informed consent 2. Patients with a known allergy to Peginterferon Lambda-1a or any component thereof 3. Display symptoms of respiratory distress (Respiratory rate >20, room air oxygen saturation of $<94\%$.) 4. Participation in a clinical trial with or use of any investigational agent within 30 days before screening 5. Treatment with interferons within 12 months before screening 6. Previous use of Peginterferon Lambda-1a 7. History or evidence of any intolerance or hypersensitivity to IFNs or other substances contained in the study medication. 8. Female patients who are pregnant or breastfeeding. Male patients must confirm that their female sexual partners are not pregnant. 9. Current or previous history of decompensated liver disease (Child-Pugh Class B or C) or hepatocellular carcinoma 10. Co-infection with human immunodeficiency virus (HIV) 11. Any of the following abnormal laboratory test results at screening:

	
c. Platelet count <75,000 cells/mm³
 
d. Absolute neutrophil count <800 cells/mm³
 
e. Hemoglobin <11 g/dL for women and <12 g/dL for men
 
f. Serum creatinine concentration $\geq 1.5 \times$ ULN and creatinine clearance (CrCl) < 50 mL/min by Cockcroft-Gault
 
12. History of liver disease other than viral hepatitis
 
13. Prior history or current evidence of any of the following:
 
 a. Immunologically mediated disease that is uncontrolled b. Retinal disorder or clinically relevant ophthalmic disorder c. Any malignancy (excluding non-melanoma skin cancer) within 5 years before screening d. Cardiomyopathy or significant ischemic cardiac or cerebrovascular disease. e. Chronic uncontrolled pulmonary disease f. Pancreatitis g. Severe or uncontrolled psychiatric disorder h. Active seizure disorder i. Bone marrow or solid organ transplantation 
14. Other significant medical condition that may require intervention during the study
 
15. Concurrent use of any of the following medications:
 
 a. Therapy with an immunomodulatory agent b. Current use of heparin or Coumadin c. Received blood products within 30 days before study randomization d. Use of hematologic growth factors within 30 days before study randomization e. Systemic antibiotics, antifungals, or antivirals for treatment of active infection within 24 hours before study randomization f. Any prescription or herbal product that is not approved by the investigator g. Long-term treatment (> 2 weeks) with agents that have a high risk for nephrotoxicity or hepatotoxicity unless it is approved by the medical monitor h. Receipt of systemic immunosuppressive therapy within 3 months before screening
Treatment assignment	Study participants will be randomly assigned 1:1 to a single subcutaneous dose of Peginterferon Lambda-1a or normal saline placebo, along with standard of care
Treatment arms	
 1. Peginterferon Lambda-1a (Lambda), 180 mcg, administered as subcutaneous injection 2. Normal saline, 0.45 ml administered as subcutaneous injection
Dose Justification	A single dose PK of Peginterferon Lambda-1a given subcutaneously has been assessed in four Phase 1 studies in healthy subjects and in two phase 2 studies in subjects with HCV. In these studies, Lambda exhibited dose-proportional PK over the dose range of 80 to 240 mcg.

	Phase 2 studies established the optimal dose for virologic suppression and minimizing treatment-related adverse events for hepatitis C at 180 mcg; this dose is also currently being used in hepatitis D trials.
Screening, enrolment, randomization, and follow-up of participants	Patients will be screened, and a baseline physical examination and laboratory assessment performed. Eligible patients will be randomized 1:1 to receive Lambda 180 mcg SC (intervention arm) or normal saline placebo (control arm) (Day 0). Patients will complete an at-home symptom questionnaire on each day of follow-up, including in-home assessments of temperature and O ₂ saturation and collection of anterior nare swabs and stool. Patients will then be seen at follow-up visits at Day 1±1, 3±1, 5±1, 7±1, 10±1, 14±1, 21±1, and 28±1. At each visit, vital signs (temperature, blood pressure, pulse rate per minute, breath rate per minute and oxygen saturation), will be performed. Efficacy of Lambda will be assessed by analysis of COVID-19 in respiratory secretions obtained by oropharyngeal swabs collected consecutively at each visit, and by anterior nare swabs collected daily at home. Clinical laboratory measurements (CBC, chemistries, LFTs) will be performed at enrollment and Days 5±1, and 14±1. Additionally, ~25 mL peripheral blood will be collected from study participants at enrollment and at Days 5±1, 14±1, and 28±1 for processing and cryopreservation into a specimen biobank. Safety and tolerability of Lambda will be assessed by adverse event (AE) monitoring, vital signs assessment and clinical laboratory tests. Patients will reach the end of study at day 28±1 of follow-up.
Primary Outcome	Duration of viral shedding of SARS-CoV-2 virus
Safety monitoring	Frequency of adverse events and serious adverse events will be analyzed in all study participants.
Planned interim analysis	An interim analysis will be performed and analyzed by a data and safety and monitoring board after 50% of study participants are enrolled and have completed 1 day of follow-up following study drug administration.
Statistical Analysis and Sample Size Considerations	We will evaluate the intention-to-treat (ITT) population, defined as the original treatment assignment groups after randomization, for the primary efficacy analysis. We will analyze the per-protocol group as supportive evidence for the primary efficacy analysis. Approximately 120 patients with COVID-19 infection are planned to be enrolled and randomized, and we conservatively assume that 90% of participants will complete follow-up. The primary endpoint will be assessed in all patients. We assume that the mean duration of virologic shedding is 14 days in individuals receiving placebo, with a standard deviation of 4 days (Zhou et al, Lancet 2020). With 60 patients randomized per arm, we will have 80% power to detect a minimum 50% reduction in virologic shedding in participants receiving Lambda.

2 BACKGROUND

2.1 SCIENTIFIC RATIONALE

[figure not shown]
2.1.1 COVID-19, a novel coronavirus with an urgent need for novel therapeutics to decrease viral shedding and transmission

Recently, a novel coronavirus has been identified as the causative pathogen of a rapidly spreading infection associated with pneumonia and severe acute respiratory syndrome. COVID-19, originally identified in Wuhan, in the Hubei province of China[1], has now spread across the globe and has been declared by the WHO as a global pandemic. While the majority of infected patients display mild symptoms if any, death rates of up to 4% due to development of severe acute respiratory syndrome (COVID-19 SARS), have been reported in patients with co-morbid conditions and in the elderly population[2]. With the unprecedented global health and economic threats imposed by COVID-19, development of therapies capable of suppressing or eradicating this emerging pathogen has become an urgent unmet medical need.

In a recent report, COVID-19+ patients presenting with mild symptoms had a median viral load of 1×10^6 copies in oropharyngeal specimens at diagnosis (an average of 2-4 days post symptom onset), and this declined in the subsequent period and correlated with resolution of symptoms[3]. All patients had evidence of viral shedding in the oropharynx 7 days following symptom onset; by day 14, 22% of patients had evidence of oropharyngeal shedding. In contrast, nearly 80% of subjects had evidence of viral shedding in both sputum and stool specimens at 14 days, in many patients outlasting the resolution of symptoms and despite the development of IgM and IgG seroconversion to the spike protein of SARS-CoV-2. These tissue-specific differences in the duration of viral shedding suggest prolonged transmissibility of SARS CoV-2 in recovered individuals. Novel therapeutics that can shorten this duration of viral shedding could be critically important in reducing transmission.

2.1.2 Peginterferon Lambda-1a, a broad-spectrum antiviral

Peginterferon Lambda-1a (hereafter referred to as Lambda) is a covalent conjugate of human recombinant non-pegylated interferon lambda and a 20-kDa linear PEG chain. Lambda is a type III interferon (i.e. IFN- λ) that stimulates innate immune responses that are critical for the development of host protection during viral infections[4]. Similar to type 1 interferons (including IFN-a), binding of IFN- λ to its cognate receptor complexes triggers signaling cascades, including those mediated by the JAK/STAT (Janus kinase/signal transducer and activator of transcription) pathway, that result in the activation of a large number of genes, many of which encode antiviral proteins (Fig 1)[5]. However, IFN- λ uses a distinct receptor complex (IL28R) for signaling which appears to be expressed on only a few cell types, including epithelial cells in the respiratory and gastrointestinal tract[4]. Based on IFN- λ 's comparable antiviral activity, more limited receptor distribution, and improved tolerability profile in comparison to IFN-a, a pegylated form of

recombinant interferon lambda (Lambda) was developed for the treatment of chronic viral hepatitis[6, 7].

Lambda was previously investigated by Bristol-Myers Squibb (BMS) for the treatment of chronic hepatitis B (HBV) and C (HCV) virus infection. This development was discontinued in 2014 based on the rapidly evolving landscape of chronic HBV and HCV treatment using non-interferon-based regimens, and not due to any new safety or efficacy findings in clinical studies. Because of the broad-spectrum antiviral activities of Lambda and fewer side effects of Lambda compared with pegylated IFN alfa-2a in HCV and HBV clinical studies, Eiger BioPharmaceuticals is investigating Lambda in the treatment of hepatitis D virus (HDV) infection, licensing worldwide rights to Lambda from BMS. Lambda has so far been administered to over 3743 patients in Phase 1, 2, and 3 clinical trials.

2.1.3 Interferons, including Lambda, for the Treatment of Respiratory Viruses including SARS-CoV

Type 1 interferons have been shown to induce inhibition of respiratory coronavirus infection[8-10]. In *in vitro* experiments, type 1 interferons were also effective in inhibiting severe acute respiratory syndrome-coronavirus (SARS-CoV)[11]. In a study of patients with SARS-CoV, a synthetic formulation of IFN- α , when given with corticosteroids, was associated with reduced disease-associated impaired oxygen saturation and resolution of radiographic lung abnormalities, in comparison with a group receiving corticosteroids alone (Figure 2)[12]. These data suggest that therapeutic use of interferon may be efficacious in the treatment of SARS-CoV.

[figure not shown]

Fig. 2 In a study of patients with SARS-CoV, patients given IFN- α and corticosteroids had improved clinical outcomes compared with patients given corticosteroids alone.

The presence of IL28R in the epithelial cells of the lungs and respiratory tract has spurred research on the potential role of IFN-λ in possible mitigation of viral induced respiratory infections. In a murine model of influenza infection, IFN-λ treatment post-infection was associated with significantly lower mortality compared to mice treated with IFN-α, and this was associated with lower influenza viral loads[13]. Furthermore, studies in animal models have shown that IFN-λ may play an important role in restricting viral replication of SARS-coronavirus (Figure 3)[14]. The use of Lambda for treatment of COVID-19 infection has to our knowledge not yet been explored.

2.2. SAFETY AND TOLERABILITY OF LAMBDA

Approximately 3,743 subjects (including 237 healthy subjects; 3,276 subjects with HCV; 197 subjects with HBV; and 50 subjects with HDV) have received Lambda to date.

In a study of healthy volunteers administered a single s.c dose of lambda up to 7.5ug/kg, reversible dose-related increases in liver transaminases (ALT and AST) were seen in 5/17 (29.4%) subjects. One of the 2 subjects treated with Lambda 7.5 μ g/kg experienced reversible Grade 3 elevation of ALT. Transaminase elevations were not associated with increases in bilirubin. Mild dose-proportional decreases in serum fibrinogen were reported for 7 subjects.

In a second healthy volunteer study, the most common AEs associated with s.c administration of lambda were abdominal pain and venous puncture site hematoma. All AEs were mild in intensity. One (3.3%) subject in the 180- μ g group had reversible Grade 1 elevations of AST and ALT not associated with clinical symptoms or bilirubin elevations.

In a recently completed 48-week study of patients with chronic hepatitis delta virus infection, treatment with 180ug lambda, 7/14 (50.0%) patients reported a Grade 3 or 4 treatment-related AE with the following frequencies: injection site reaction 1 (7.1%), ALT or AST increase 5 (35.7%), bilirubin increase 2 (14.3%), decreased neutrophil count 1 (7.1%), flu-like symptoms including fever/chills 9 (64.3%), arthralgia or myalgia 7 (50.0%) and fatigue 8 (57.1%). At the end-of-treatment ALT or AST $>5\times$ ULN $<10\times$ ULN was reported in a single patient. There were no increases in bilirubin $>2\times$ ULN concurrent with increases in ALT or AST at the end-of-treatment. In other studies of lambda as a combination therapy for hepatitis B or C, clinically meaningful increases in total bilirubin occurred in 7.6% and 2.6% of patients dosed with Lambda/Ribavirin (RBV) and Lambda/RBV/Daclatasvir (DCV), respectively. Similarly, increases in serum ALT were noted in 6.2% and 3.7% of subjects on Lambda/RBV and Lambda/RBV/DCV, respectively. All increases were manageable with dose withholding, reduction, or discontinuation.

Lymphopenia was not seen with any significance in prior Lambda studies of 48 weeks. Pyrexia occurred at a frequency of 9.9% of patients treated with the 180ug lambda + RBV.

IFN-based treatment induces a variety of psychiatric adverse effects, including depression, manic condition, acute and chronic cognitive dysfunction, suicidal behavior, and relapse of

[figure not shown]

Fig. 3 In comparison to wild-type mice, mice lacking IFN-λ or IFN-α had impaired viral restriction against SARS-CoV.

substance abuse. These effects are observed with a much lower frequency than seen with interferon alpha.

Injection site reactions including erythema, irritation, inflammation, rash, eczema, pruritus, dryness, swelling, and hematoma have been reported (range: 2–15%).

2.3 DOSAGE JUSTIFICATION

The single dose PK of Peginterferon Lambda-1a given subcutaneously has been assessed in four Phase 1 studies in healthy subjects and in two phase 2 studies in subjects with HCV. In these studies, Lambda exhibited dose-proportional PK over the dose range of 80 to 240 mcg. Phase 2 studies established the optimal dose for virologic suppression and minimizing treatment-related adverse events for hepatitis C at 180 mcg; this dose is also currently being used in hepatitis D trials.

2.4 RISK/BENEFIT ASSESSMENT

As no known effective treatment is available for COVID-19, participants may have access to effective therapy in the trial. They may have the added benefit of reducing household and community transmission of the virus

3. STUDY OBJECTIVES

3.1 Primary objective

- To evaluate the efficacy of subcutaneous injections of a single dose of 180 mcg of Peginterferon Lambda-1a compared with placebo in reducing the duration of viral shedding of SARS-CoV-2 virus in patients with uncomplicated COVID-19 disease.

3.2. Secondary objectives

- To evaluate the efficacy of subcutaneous injection of a single dose of 180 mcg of Peginterferon Lambda-1a compared with placebo, in reducing the duration of symptoms, hospitalizations, or ED visits in patients with uncomplicated COVID-19 disease.
- To evaluate the safety and tolerability of subcutaneous injection of a single dose of 180 mcg of Peginterferon Lambda-1a compared with placebo.

4. STUDY DESIGN

4.1 Study overview

This is a single center, open-label randomized controlled trial. Each subject will be administered either a single subcutaneous dose of study drug or placebo.

Screening data will be reviewed to determine subject eligibility. Subjects who meet all inclusion criteria and none of the exclusion criteria will be entered into the study

The following treatment regimens will be used:

- Experimental treatment: Peginterferon Lambda-1a, 180 mcg subcutaneous
- Control treatment: Normal saline, 0.45 mL subcutaneous

The duration of participation for each individual will be up to 28 days, with optional follow-up to 10 months following randomization. The planned duration for the entire study is 12 months.

5. CRITERIA FOR EVALUATION

5.1. Primary efficacy endpoint

- Time to first of two consecutive negative oropharyngeal tests for SARS-CoV-2 by qRT-PCR.

5.2. Secondary efficacy endpoints

- SARS-CoV-2 RNA levels during follow-up
- SARS-CoV-2 viral load area under the curve
- Time to alleviation of all symptoms (fever, chills, cough, nasal congestion, muscle pains), defined as the time from initiation of treatment until all symptoms are rated as absent or mild in symptomatic patients
- Incidence of emergency department visits or hospitalizations within 28 days of initiation of treatment

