6.2 Inclusion Criteria

Patients must fulfill all of the following inclusion criteria to be eligible for the study:

1. Age \geq 18 years and \leq 75 years at the time of the assessment
2. Able and willing to understand the study, adhere to all study procedures, and provide written informed consent
3. Diagnosis of COVID-19 disease:
 - a. If symptomatic, presence of mild to moderate symptoms without signs of respiratory distress, with FDA-cleared molecular diagnostic assay positive for SARS-CoV-2 within 72 hours from swab to the time of commencing informed consent:
 - b. If asymptomatic, initial diagnosis of SARS-CoV-2 infection with positive FDA-cleared molecular diagnostic assay obtained no more than 72 hours from initial swab to the time of commencing informed consent

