12.4 Analysis of secondary endpoints

SARS-CoV2 Log₁₀ viral loads at follow-up timepoints will be compared between groups using the Wilcoxon rank-sum test and/or generalized estimating equations with robust standard errors. The area-under-the-curve (AUC) SARS-CoV2 viral RNA levels during follow-up will be estimated using the linear trapezoidal method, and mean AUC levels compared between groups using the Wilcoxon rank-sum test.

The distribution of cessation of symptoms will be estimated using the Kaplan-Meier method, and Kaplan-Meier curves will be presented for each treatment arm. Time to cessation of symptoms at the end of the study period along with 95% confidence intervals will be presented for each treatment arm. The hazard ratio for cessation of symptoms will be estimated, along with its 95% confidence intervals, from a Cox proportional hazards model. Time to cessation of symptoms will be estimated in the subgroup of patients who are symptomatic at baseline.

The incidence of hospitalizations and emergency department visits will be compared between groups using negative binomial regression models, which will account for differing follow-up times through an offset term.

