## 1 STUDY DETAILS

### 1.1 Study design

This phase 2 randomized, single-blind study intends to evaluate the efficacy of a single dose of peginterferon lambda-1a in outpatients with mild COVID-19 compared with placebo in reducing the duration of shedding of SARS-CoV-2 virus.

One hundred and twenty (60 per arm) enrolled patients will be randomized in a 1:1 fashion. Thus, there will be two arms: (1) the control arm, comprised of placebo in addition to standard supportive care and (2) the treatment arm, comprised of a single dose of peginterferon lambda-1a in addition to standard supportive care. An interim analysis for safety and overwhelming efficacy will be performed once 50% of patients have 24 hours of follow-up complete.

The primary analysis is based on intent-to-treat principles in that all patients who are randomized to study arm are included in the analysis, where cessation of shedding is assessed according to randomized study arm. The secondary analysis of adverse events (AE) are assessed according to dose received.

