### **2.4 Secondary efficacy analyses**

Time to resolution of all symptoms will be defined as the time from randomization until the first study day in which no symptoms are reported. The distribution of time to resolution of symptoms will be estimated using the Kaplan-Meier method, and Kaplan-Meier curves will be presented for each treatment arm. Time to symptom resolution at the end of the study period along with 95% confidence intervals will be presented for each treatment arm. The hazard ratio for resolution of symptoms will be estimated, along with its 95% confidence intervals, from a Cox proportional hazards model adjusted for age and sex.

We will model SARS-CoV-2 viral load in oropharyngeal tests over time using a generalized mixed effects linear regression model with a random effect for study participant to account for correlation within a participant. Viral load with cycle threshold (Ct) values above the limit of detection will be calculated by substituting a Ct value of 42 into the equation  $10^{(Ct - 42) * 0.23}$  to derive viral load from Ct. A logarithmic transformation on viral load will be fit to treatment arm, time, armXtime, and adjusted for age and sex to account for therandomization stratification variables. The armXtime interaction term will allow us to assess whether the trajectory of viral load differs by treatment arm. Time will be defined as days from randomization and, depending on model fit, will either be modeled continuously or with a flexible approach allowing a non-linear trajectory for the change in viral load over time. Model fit will be assessed based on visual inspection of the residuals. Alternative transformations or generalized linear models with a link function besides the identity link will be considered if the model does not fit the data well.

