## 2.5 Exploratory efficacy analyses

An alternative definition of the secondary endpoint of symptom resolution will be considered in an exploratory analysis. We will evaluate time to sustained symptom resolution, defined as time from randomization until the first day in which no symptoms are reported and are not reported for the duration of the study. The analysis of time to sustained symptom resolution will follow the methods described for the secondary endpoint evaluation symptom resolution in the previous section. Time to symptom resolution based on symptom subsets (i.e. respiratory, systemic) will be similarly analyzed, additionally excluding participants who did not report symptoms from the specified subset at screening.

Time to disease progression will be defined as the time from randomization until the first day of a two point or more increase in either cough or shortness of breath persisting for at least 48 hours or an increase to a score of 4 or 5, or first day of admission to the emergency department, hospitalization, or death. Analysis and reporting of results will be done following methods detailed for time to symptom resolution.

Freedom from SARS-CoV-2 infection by oropharyngeal and nasal swabs at Day 5, 7, 10, and 14 will be modeled using a multivariable logistic regression model adjusted for age and sex. The odds ratio will be presented along with its 95% confidence interval.

Similar approaches to those used for evaluating SARS-CoV-2 viral load in oropharyngeal tests over time and AUC will be used to evaluate viral load in nasal tests.

Correlation between virology and symptomology will be characterized by evaluating the relationship between CT values obtained from the oropharyngeal tests and each symptom through two main approaches. For symptoms graded on an ordinal scale, we will calculate a Spearman correlation and assess significance with a Z-test. For variables that capture presence of a symptom, differences in the median CT values by presence or absence of the symptom will be presented and assessed via a Wilcoxon rank sum test.

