## 3 HANDLING OF MISSING AND CENSORED DATA

All efforts will be made to minimize instances of missing data. However, we expect some missing data will occur. Our analyses will assume data are missing at random. For the primary endpoint of time to shedding cessation, any participant who drops out prior to having two consecutive negative tests will be censored at their last positive test. Participants who have no post-randomization test results available or a single test result that is negative will be censored at day 1. Similarly, participants will be right censored for the time to symptom resolution or progression at the time when their last symptom questionnaire is completed. Participants who are asymptomatic at screening and never report symptoms thereafter will be considered to have met symptom resolution at study Day 1. For other missing data, we will use multiple imputation-based analyses. This approach will be applied to any analysis involving endpoints or key

variables where any missing data occurs in order to adhere to the ITT principle. Sensitivity to assumptions regarding missingness will be addressed through sensitivity analyses.

If more than 5% of participants do not have the time of shedding cessation observed (i.e. they are right-censored), we will perform a sensitivity analysis to evaluate the robustness of our findings to missing data assumptions. In the sensitivity analysis, among those missing timing of shedding cessation, we will assume varying proportions (e.g. 25%, 50%) of participants in each arm who would have ceased shedding by Day 28. The proportions will differ by arm so we can evaluate whether our findings stand if it were true that people who dropped out stopped shedding earlier in the placebo arm vs the active arm.

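### Protocol 5.2 and the SAP define the same secondary symptom endpoint differently, and each rule gives some patients an automatic event at or near time zero

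*Protocol*

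**What the plan says.** The two documents describe one secondary endpoint in different terms.

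- **Protocol 5.2** names it as "Time to alleviation of all symptoms (fever, chills, cough, nasal congestion, muscle pains") and times it as "defined as the time from initiation of treatment until all symptoms are rated as absent or mild in symptomatic patients".
- **Protocol 6.2, criterion 3a** sets the entry range: "If symptomatic, presence of mild to moderate symptoms without signs of respiratory distress". It does not require any symptom to be moderate.
- **Protocol 12.4** calls the event cessation of symptoms, does not define that term, and limits the set: "Time to cessation of symptoms will be estimated in the subgroup of patients who are symptomatic at baseline".
- **SAP 2.4** defines the event as "the time from randomization until the first study day in which no symptoms are reported".
- **SAP 2.5** has a sustained version, exploratory only: "first day in which no symptoms are reported and are not reported for the duration of the study".
- **SAP section 3** adds: "Participants who are asymptomatic at screening and never report symptoms thereafter will be considered to have met symptom resolution at study Day 1".

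SAP 1.1 describes the population as "in outpatients with mild COVID-19 compared with placebo". Neither document gives the distribution of symptom severity at entry, or a power target for this endpoint.

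**The concern.** The Protocol 5.2 threshold lies inside the entry range. A patient whose worst listed symptom is mild qualifies for the trial and meets the endpoint at the same moment. So does a patient whose only complaints fall outside the five listed symptoms, such as the sore throat, headache, fatigue or shortness of breath that SAP 1.4 tracks. Nothing in Protocol 5.2 asks for a minimum severity at baseline or a minimum change.

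The SAP has a different weakness of the same kind. A participant who never has symptoms cannot show resolution, yet is counted as resolved at Day 1.

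In both cases randomization spreads the automatic events evenly on average, so they do not create a false treatment effect. They do pull the hazard ratio toward 1, shorten both medians and cost power. Because both definitions are current, the result reported for this endpoint also depends on which document is followed.

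**Working it through.** **Step 1. The definitions side by side.**

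| Element | Protocol 5.2 / 12.4 | SAP 2.4 / section 3 |
|---|---|---|
| Threshold | Mild counts as met | No symptoms |
| Clock starts | Initiation of treatment | Randomization |
| Symptoms | Five listed | All reported |
| Analysis set | Symptomatic patients only | Never-symptomatic included, event at Day 1 |

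The documents differ on all four elements. With a single dose on Day 0 the clock difference should be small numerically, but it matters for anyone randomized and not dosed.

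**Step 2. Who has an automatic event.**

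- Symptomatic, nothing above mild among the five: time zero under Protocol 5.2; not yet an event under SAP 2.4.
- Symptomatic only outside the five: time zero under Protocol 5.2; not yet an event under SAP 2.4.
- Never symptomatic: outside the Protocol analysis; event at Day 1 under the SAP.

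**Step 3. Effect on the curve.** There is no plan figure to reproduce here. Let q be the share already at the threshold and S*(t) the curve for patients truly at risk. The observed curve is S(t) = (1 − q) × S*(t), so the observed median solves S*(t) = 0.5/(1 − q).

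The following inputs are assumptions, not plan figures: 54 symptomatic patients per arm (90% of 60), Weibull shape 1.5, control median 6 days, true hazard ratio 1.7, daily readings to Day 28.

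- q = 0: control median 6 days; treated 6 × (1/1.7)^(2/3) = 4.2 days; gap 1.8 days.
- q = 0.3: 0.5/0.7 = 0.714, and −ln(0.714)/ln 2 = 0.485. Control 6 × 0.485^(2/3) = 3.7 days; treated 6 × (0.485/1.7)^(2/3) = 2.6 days; gap 1.1 days.
- q of 0.5 or more: the median is zero in both arms.

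At q = 0.3, 54 × 0.3 = 16.2 patients per arm have an event before treatment can act, and 54 × 0.7 = 37.8 remain informative.

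**Step 4. Effect on the hazard ratio and power.** Simulation under the same assumptions, with the Cox model (Efron ties) for the hazard ratio and the log-rank test for power. Ranges show the spread between runs.

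| Share q | Cox HR, all symptomatic | Power, all symptomatic | Power, at-risk only |
|---|---|---|---|
| 0% | 1.73 | – | – |
| 30% | 1.44 | 45–48% | 60–61% |
| 50% | 1.28–1.29 | 27–29% | 44–45% |
| 70% | 1.15 | 16–17% | 31–32% |

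Dropping patients who cannot respond raises power although the set is smaller. A second simulation with other assumptions (60 per arm, exponential times, control median 8 days, true hazard ratio 2.03) shows the same direction: power 97% at q = 0, 64% at 40% and 17% at 80%.

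**The case against.** The strongest reply is that the SAP presents itself as the detailed description of the analysis, and its secondary endpoint needs a symptom-free day. A patient with mild symptoms has not met that event. A reader might infer from Protocol 5.2 that the planned symptom analysis is swamped by events at time zero. The documents do not support that: the mild-at-entry problem does not reach SAP 2.4. This part of the reply stands.

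A reader might also infer from a trial in mild disease that many patients start at the threshold. That is plausible but undocumented. Criterion 3a can be read as an overall clinical description, whereas Protocol 5.2 concerns ratings of individual symptoms, and the questionnaire's rating anchors are not in the text available. This part stands too, so the figures above are hypothetical.

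Nor is the lack of a confirmation rule an error in itself. SAP 2.5 already analyses sustained resolution, as an exploratory endpoint, and requiring two consecutive days would be a design preference.

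Two things remain. The SAP does not withdraw the Protocol definition, although its revision history says it was updated to match the protocol. And the SAP carries its own automatic event at Day 1. SAP 2.7 does plan a subgroup limited to patients with symptoms at baseline, but it names only the primary endpoint. Its closing extension to other key endpoints refers to sensitivity and effect-modification analyses.

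**Conclusion.** The point holds as a conflict between two definitions of one secondary endpoint, each with a group of uninformative events. Protocol 5.2 is defective as written, because its threshold overlaps the entry criterion and the baseline restriction in 12.4 does not cure it. SAP 2.4 has the sounder threshold, but section 3 admits never-symptomatic participants as Day 1 events, against Protocol 5.2 and 12.4.

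The size is unknown. At an assumed 30% share, and under the other assumptions listed, a true hazard ratio of 1.7 would be estimated at about 1.44, with power about 45–48% against about 60% in at-risk patients. Those figures describe what following Protocol 5.2 could cost; they do not forecast the SAP analysis. The Day 1 rule dilutes by the same mechanism, to a degree set by the never-symptomatic share, which the documents also do not give. The primary endpoint is not affected.

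**What to change.** 1. In Protocol 5.2, replace the threshold with the SAP 2.4 definition: first day with no symptoms, counted from randomization. Use the same term in 12.4.
2. In both documents, restrict this analysis to participants symptomatic at baseline, and state which pre-dose assessment decides that.
3. In SAP section 3, drop the Day 1 event for never-symptomatic participants from this analysis. SAP 2.5 already excludes participants without the relevant symptoms at screening from its symptom-subset analyses, so the principle is in the plan.
4. If the Protocol 5.2 threshold is kept as an additional endpoint, analyse only participants with at least one listed symptom above mild at Day 0. This needs severity ratings taken before dosing; the text available does not show whether the Day 0 assessment records them.
5. A two-day confirmation rule is optional.

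The cost of items 1 to 3 is wording: daily questionnaires through Day 28 are already planned. The analysis set becomes smaller, and participants who develop symptoms only after baseline leave this comparison and can be described separately. Selection on a pre-randomization characteristic keeps the randomized comparison intact. Under item 4 the set shrinks further, but the patients removed could not have responded.
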